### **Statement of Compliance to protocol, GCP and applicable regulatory guidelines:**

This trial will be conducted in compliance with the protocol, ISO 14155, the International Conference on Harmonization Good Clinical Practice E6 (ICH-GCP), the Declaration of Helsinki, and all applicable regulatory requirements.

## CHANGE HISTORY

Version	Originator	Description of Change(s) and Section Number(s) Affected	Date
1.0	[name]	Original Protocol	24 September 2018

**SYNOPSIS**

Protocol Title	An investigation of the impact of localized topical anesthesia of the ocular surface on end-of-day contact lens discomfort.
Sponsor	JJVC, [name]
Clinical Phase	Development phase, phase 0
Trial Registration	This study will be registered on ClinicalTrials.gov
Test Article(s)	None (habitual contact lenses)
Wear and Replacement Schedules	Habitual lenses will be worn for 14 ± 2 hours on study days
Objectives	
Primary Objective To evaluate the effect of topical anesthesia of the upper lid margin, lower lid margin and cornea on end-of-day discomfort in symptomatic contact lens wearers.
 
Secondary Objective To determine the effect of contact lens removal on end-of-day discomfort in symptomatic soft contact lens wearers.

Study Endpoints	
Primary endpoint: Subjective scores of comfort (VAS scale) collected at various time points:
 
 
• Immediately prior to lens application
 
• 5 minutes after lens application
 
• 14 hours after lens application (i.e. pre-treatment)
 
• Immediately after lens removal prior to treatment application, only for the cornea.
 
• 5 minutes post-treatment
 
• 10 minutes post-treatment
 
 
Other observations: none.

Study Design	
This is a controlled, randomized, subject-masked, 3x3 crossover, non-dispensing, contralateral study. Twenty subjects will be recruited based on their scores (with their habitual lenses) from the Contact Lens Dry Eye Questionnaire-8 (CLDEQ-8 score of 20-37) and examined on four occasions:
 
Visit 1: Screening  Visit 2-4: At each study visit, an ocular region (upper lid margin, lower lid margin or cornea) will be anesthetized on one eye, whilst the fellow eye will receive a saline placebo treatment at the same ocular location. Subjective comfort scores (VAS scale) will be collected prior to and following the treatment on each eye.
 
See the flow chart at the end of the synopsis table for the schematic of the study visits and procedures of main observations (Figure 1).

Sample Size	Up to 20 eligible subjects will be enrolled into the study with a target of 15 to complete.
Study Duration	Five months
Anticipated Study Population	Habitual soft contact lens wearers aged 18 and above who are classified as symptomatic based on a CLDEQ-8 score of 20-37
Eligibility Criteria	
Potential subjects must satisfy all of the following criteria to be enrolled in the study:
 
Inclusion Criteria after Screening
 
 
1. They are of legal age (18 years) and capacity of volunteer.
 
2. The subject must read, understand, and sign the STATEMENT OF INFORMED CONSENT and receive a fully executed copy of the form.
 
3. They must appear able and willing to adhere to the instructions set forth in this clinical protocol.
 
4. They have worn the same brand of soft spherical contact lenses for at least the previous three months, by self-report.
 
5. They are defined as ‘symptomatic’ contact lens wearers (CLDEQ-8 score of 20-37) with their habitual contact lenses.
 
6. They are willing to wear their lenses for approximately 14 hours on study days.
 
7. They have a wearable pair of spectacles, if applicable.
 
8. They agree not to participate in other clinical research
 

for the duration of this study.

Inclusion Criteria after Baseline

9. They can attain high contrast logMAR visual acuity of 0.20 or better in their habitual contact lenses in each eye.

Potential subjects who meet any of the following criteria will be excluded from participating in the study:

Exclusion Criteria after Screening:

[figure not shown]
1. They have an ocular disorder, which would normally contra-indicate contact lens wear.
2. They have a systemic disorder, which would normally contra-indicate contact lens wear.
3. They are using any topical medication such as eye drops or ointment.
4. They have had cataract or corneal refractive surgery.
5. They are pregnant or breast-feeding by self-report.
6. They have any infectious disease (e.g. hepatitis) or any immunosuppressive disease (e.g. HIV), by self-report.
7. They have any known hypersensitivity or allergic reaction to any of the known ingredients in the anesthetic.
8. They have a history of severe allergic reaction or anaphylaxis.
9. They have a history of cardiac disease or hyperthyroidism.
10. They have taken part in any other contact lens or care solution clinical trial or research, within two weeks prior to starting this study.
11. They are an employee or immediate family member of an employee of clinical site (e.g., Investigator, Coordinator, Technician).

Exclusion Criteria after Baseline

[figure not shown]
12. They have any corneal distortion resulting from previous hard or rigid lens wear or have keratoconus.
13. They have grade 3 or greater of any of the following ocular surface signs which would contraindicate contact lens wear: corneal oedema, corneal vascularisation, corneal staining, tarsal conjunctival changes or any other abnormality which would normally contraindicate contact lens wear.

Disallowed Medications/Interventions	No ocular topical medications No systemic medications that in the view of the investigator may affect the ocular surface or contact lens wear from 24 hours prior to study visits
Measurements and Procedures	Subjective comfort scores (VAS scale) and safety parameters (visual acuity and biomicroscopy)
Microbiology or Other Laboratory Testing	None
Study Termination	The occurrence of one or more Unanticipated Serious Adverse Device Effect (USADE), or any SAE where relationship to study agent cannot be ruled out, will result in stopping further study procedures. In the event of a UADE or SAE, the Sponsor Medical Monitor may unmask the treatment regimen of subject(s) and may discuss this with the Principal Investigator before any further subjects are enrolled.
Ancillary Supplies/ Study-Specific Materials	Topical anesthetic: proxymetacaine hydrochloride 0.5% (Chauvin Pharmaceuticals Ltd) Crest Medical Ltd Saline Pods (or other sponsor-approved material)
Principal Investigator(s) and Study Institution(s)/Site(s)	A full list of Principal Investigators, clinical sites, and institutions is kept separately from the Study Protocol and is included in the study Trial Master File.

Figure 1: Study Flowchart

## COMMONLY USED ABBREVIATIONS AND DEFINITIONS OF TERMS

ADD	Plus Power Required For Near Use
ADE	Adverse Device Effect
AE	Adverse Event/Adverse Experience
BCVA	Best Corrected Visual Acuity
BSCVA	Best Spectacle Corrected Visual Acuity
CFR	Code of Federal Regulations
CLUE	Contact Lens User Experience
COAS	Complete Ophthalmic Analysis System
COM	Clinical Operations Manager
CRA	Clinical Research Associate
CRF	Case Report Form
CRO	Contract Research Organization
CT	Center Thickness
	
D	Diopter
DMC	Data Monitoring Committee
eCRF	Electronic Case Report Form
EDC	Electronic Data Capture
ETDRS	Early Treatment Diabetic Retinopathy Study
FDA	Food and Drug Administration
GCP	Good Clinical Practice
HIPAA	Health Insurance Portability and Accountability Act
IB	Investigator's Brochure
ICF	Informed Consent Form
ICH	International Conference on Harmonization
IDE	Investigational Device Exemption
IEC	Independent Ethics Committee
IRB	Institutional Review Board
ISO	International Organization for Standardization
ITT	Intent-to-Treat
JJVC	Johnson & Johnson Vision Care, Inc.
LC	Limbus Center
LogMAR	Logarithm of Minimal Angle of Resolution
MedDRA ®	Medical Dictionary for Regulatory Activities
MOP	Manual of Procedures
NIH	National Institutes of Health
OD	Right Eye
OHRP	Office for Human Research Protections
OHSR	Office for Human Subjects Research
OS	Left Eye
OU	Both Eyes
PD	Protocol Deviation
PHI	Protected Health Information
PI	Principal Investigator
PIG	Patient Instruction Guide

PQC	Product Quality Complaint
PRO	Patient Reported Outcome
QA	Quality Assurance
QC	Quality Control
SAE	Serious Adverse Event/Serious Adverse Experience
SAP	Statistical Analysis Plan
SAS	Statistical Analysis System
SD	Standard Deviation
SOP	Standard Operating Procedure
UADE	Unanticipated Adverse Device Effect
USADE	Unanticipated Serious Adverse Device Effect
VA	Visual Acuity

## 1. INTRODUCTION AND BACKGROUND

Previous work [REDACTED] has shown that we are able to successfully and selectively anesthetize the entire cornea, upper lid margin and lower lid margin in the majority of subjects whilst keeping the other ocular regions relatively unaffected. Isolating specific regions of the anterior ocular surface in this manner is potentially useful for systematically investigating whether or not contact lens discomfort can be improved when any of these areas are ‘numbed’.

The aim of this study is to evaluate the effect of topical anesthesia on the upper eyelid margin, lower eyelid margin and the cornea in wearers suffering from end-of-day contact lens discomfort.

### 1.1. Name and Descriptions of Investigational Products

The following products will be used in this study:

- Single use Minims of proxymetacaine hydrochloride, 0.5% (a commercially available topical anesthetic) will be used to temporarily numb selective areas of the ocular surface (lower lid margin, upper lid margin and cornea).
- Sodium chloride 0.9% will be used as a placebo treatment.

### 1.2. Intended Use of Investigational Products

The intended use of proxymetacaine hydrochloride, 0.5% is to numb selective areas of the ocular surface. It is a topical ocular anesthetic. Typically, a drop which is ~30µl in size is used to numb the cornea in everyday clinical practice but in this work smaller amounts than this will be used in one eye on three different study days. The amounts used are detailed in the Eurolens Research Standard Operating Procedure ‘Procedure for selectively anaesthetizing the cornea and eyelid margins’ (Appendix D).

Sodium chloride 0.9% will be used as a placebo treatment in one eye on three different study days.

### **1.3. Summary of Findings from Nonclinical Studies**

Not Applicable – Marketed product only.

### **1.4. Summary of Known Risks and Benefits to Human Subjects**

There is no direct benefit to the subject from participation in the study. The information obtained from this study will aid in the development of improved contact lenses in the future.

Proxymetacaine hydrochloride, 0.5%: see electronic Medicines Compendium (eMC) entry for this drug (Summary of Product Characteristics) and the Patient Information leaflet in Appendix C.

Sodium chloride 0.9%: see Material Safety Data Sheet in Appendix C.

### **1.5. Relevant Literature References and Prior Clinical Data Relevant to Proposed Clinical Study**

One previously completed sponsored clinical study:

[name]. *Clinical Study Report #(VIS-CR-5876) Project Lennon: Understanding Contact Lens Comfort*. June 6, 2017. 

Also, previous pilot work on anesthetizing parts of the ocular surface was presented at the following conference:

[name], [name] and [name]. Effect of selective topical anesthesia on initial comfort of rigid contact lenses. British Contact Lens Association 39th Annual Clinical Conference and Exhibition. May 29-31, 2015, ACC, Liverpool, UK. 

## **2. STUDY OBJECTIVES, ENDPOINTS AND HYPOTHESES**

### **2.1. Objectives**

#### **Primary Objective**

To evaluate the effect of topical anesthesia of the upper lid margin, lower lid margin and cornea on end-of-day discomfort in symptomatic contact lens wearers.

#### **Secondary Objective**

To determine the effect of contact lens removal on end-of-day discomfort in symptomatic soft contact lens wearers.

## 2.2. Endpoints

### Primary Endpoint(s)

The primary endpoint is the subjective scores of comfort (VAS scale) collected at various time points:

- Immediately prior to lens application
- 5 minutes after lens application
- 14 hours after lens application (i.e. pre-treatment)
- Immediately after lens removal prior to treatment application, only for the cornea.
- 5 minutes post-treatment
- 10 minutes post-treatment

## 2.3. Hypotheses

### Primary Hypotheses

1. Post-treatment subjective scores of comfort (VAS scale) for anesthetized eyes are superior to eyes that received the placebo for at least one of the ocular regions (upper lid margin, lower lid margin, or cornea).
2. Comfort change from pre-treatment for anesthetized eyes is superior to eyes that received the placebo for at least one of the ocular regions (upper lid margin, lower lid margin, or cornea).
3. Post-treatment subjective scores of comfort (VAS scale) for anesthetized eyes are equivalent to 5-minute post lens application levels in the morning for at least one of the ocular regions (upper lid margin, lower lid margin, or cornea). An equivalence margin of 10 points will be used.

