## 14.2. Sample Size Justification

The plan is to enroll 20 subjects with a target of 15 subjects to complete the study. This is a pilot study and the sample size was not based on any empirical power calculation.

The tables below, provided using the POWER procedure in SAS 9.4, summarizes statistical power based on the following assumptions:

- Testing for superiority with 0 VAS points and equivalence with +/- 10 VAS points
- True difference for superiority: 5, 7.5, 10 points and for equivalence: -5, 0, -5 points
- Estimated standard deviations of 15 and 20 points
- Intraclass correlations of 0.4, 0.6, and 0.8
- Two-sided type I error rate of 0.05
- 15 subjects successfully complete the study

Table 3: Power Analysis for the Primary Hypothesis (Superiority)

Difference (Test-Control)	Estimated Standard Deviation	Intraclass Correlation		
		0.4	0.6	0.8
5.0	15	0.300	0.393	0.617
5.0	20	0.211	0.269	0.425
7.5	15	0.515	0.661	0.897
7.5	20	0.351	0.460	0.705
10.0	15	0.724	0.864	0.987
10.0	20	0.515	0.661	0.897

The study is appropriately powered (power above 80%) to show superiority of anesthetized eyes over eyes that received the placebo when the difference in VAS comfort is at least 7.5 points and the intraclass correlation is at least 0.8.

Table 4: Power Analysis for the Primary Hypothesis (Equivalence)

Difference (Test-Control)	Estimated Standard Deviation	Intraclass Correlation		
		0.4	0.6	0.8
-5.0	15	0.259	0.386	0.617
-5.0	20	0.081	0.202	0.422
0.0	15	0.453	0.728	0.974

Difference (Test-Control)	Estimated Standard Deviation	Intraclass Correlation		
		0.4	0.6	0.8
0.0	20	0.117	0.334	0.794
5.0	15	0.259	0.386	0.617
5.0	20	0.081	0.202	0.422

The study is appropriately powered (power above 80%) to show equivalence between comfort scores at post-treatment and 5-minute post-application when there is no difference (0 VAS points) and the intraclass correlation is at least 0.8.

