### 14.4. Level of Statistical Significance

All planned analysis for this study will be conducted with an overall type I error rate of 5%.

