### 14.5. Primary Analysis

#### VAS Comfort

VAS Comfort score at 5 and 10 minutes post treatment will be analyzed separately using a linear mixed model. The model will include the following experimental design factors: treatment, sequence of treatment, region, sequence of region, period, time event, and first-order carryover as fixed effects. Baseline characteristics such as age and gender may be included as covariates when appropriate. The covariance between residual errors for the same subject across periods will be modeled using one of the following covariance structures: Compound Symmetry (CS) or Unstructured (UN). The covariance structure that returns the lowest Akaike Information Criteria Corrected (AICC) will be selected as the structure that best fits the data. The Kenward and Roger method will be used for the calculation of denominator degrees of freedom.

The null and alternative hypothesis for superiority of anesthetized eyes compared to eyes that received the placebo with respect to VAS comfort at post treatment, where  $\mu_A - \mu_P$  is the difference in VAS comfort between anesthesia and placebo treatments, is as follows:

$$\begin{aligned}H_0: \mu_A - \mu_P &\leq 0 \\H_A: \mu_A - \mu_P &> 0\end{aligned}$$

The hypothesis will be tested via corresponding two-sided 95% confidence interval for least-squares mean difference (anesthesia minus placebo) of VAS comfort. Superiority will be concluded if the lower limit is greater than 0 for at least one of the three ocular regions (upper lid margin, lower lid margin, or cornea).

The null and alternative hypothesis for equivalence of VAS comfort scores at post-treatment and 5-minutes post-application, where  $\mu_1 - \mu_2$  is the difference in VAS comfort score between post-treatment and 5-minutes post-application, is as follows:

$$\begin{aligned}H_0: |\mu_1 - \mu_2| &\geq 10 \\H_A: |\mu_1 - \mu_2| &< 10\end{aligned}$$

The hypothesis will be tested via corresponding two-sided 95% confidence interval for least-squares mean difference (post treatment minus post application) in VAS comfort score. Equivalence will be concluded if the upper limit is less than 10 and the lower limit is greater than  $-10$ .

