### VAS Comfort (Change)

VAS Comfort score change from pre-treatment to 5 and 10 minute post-treatment values will be analyzed separately using a linear mixed model. The model will include the following experimental design factors: treatment, sequence of treatment, region, sequence of region, period, and first-order carryover as fixed effects; subject as a random effect. Baseline characteristics such as age and gender may be included as covariates when appropriate. The covariance between residual errors for the same subject across periods will be modeled using one of the following covariance structures: Compound Symmetry (CS) or Unstructured (UN). The covariance structure that returns the lowest Akaike Information Criteria Corrected (AICC) will be selected as the structure that best fits the data. The Kenward and Roger method will be used for the calculation of denominator degrees of freedom.

The null and alternative hypothesis for superiority of anesthetized eyes compared to eyes that received the placebo with respect to VAS comfort change from pre-treatment, where  $\Delta_A - \Delta_P$  is the difference in VAS comfort change from pre-treatment between anesthesia and placebo treatments, is as follows:

$$\begin{aligned}H_0: \Delta_A - \Delta_P &\leq 0 \\H_A: \Delta_A - \Delta_P &> 0\end{aligned}$$

The hypothesis will be tested via corresponding two-sided 95% confidence interval for least-squares mean difference (anesthesia minus placebo) of VAS comfort change from pre-treatment. Superiority will be concluded if the lower limit is greater than 0 for at least one of the three ocular regions (upper lid margin, lower lid margin, or cornea).

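### Primary hypotheses 1 (raw score) and 2 (change score) test the same anesthesia effect at full alpha with no rule for which decides; if either suffices, the false-positive chance rises about 1.7 to 1.9 times

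*Combined protocol and SAP*

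**What the plan says.** Protocol section 2.3 lists three primary hypotheses. The first concerns the score after treatment: "Post-treatment subjective scores of comfort (VAS scale) for anesthetized eyes are superior to eyes that received the placebo for at least one of the ocular" (the list of three follows). The second concerns the change in that score: "Comfort change from pre-treatment for anesthetized eyes is superior to eyes that received the placebo for at least one of the ocular regions".

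Section 14.5 gives each its own model and decision rule. For the raw score: "The hypothesis will be tested via corresponding two-sided 95% confidence interval for least-squares mean difference (anesthesia minus placebo) of VAS comfort". For the change score the criterion is a "two-sided 95% confidence interval for least-squares mean difference (anesthesia minus placebo) of VAS comfort change from pre-treatment". The success rule has the same wording in both parts: "Superiority will be concluded if the lower limit is greater than 0 for at least one of the three ocular regions". Each scale is analyzed separately at 5 and at 10 minutes.

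Section 14.4 states: "All planned analysis for this study will be conducted with an overall type I error rate of 5" per cent. Section 14.2 lists among its power assumptions: "Two-sided type I error rate of 0.05".

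Section 5.1 randomizes anesthesia and placebo to the two eyes within each region. The protocol gives no order of testing, alpha split, gatekeeping or either/both rule for hypotheses 1 and 2, and does not say which prevails if they differ.

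**The concern.** Because treatment is randomized to eye, the expected between-eye difference before treatment is zero. The raw difference and the difference in change therefore have the same expected value. They are two estimators of one effect, and both carry primary status at the full level.

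Two things follow. First, section 14.5 lets each scale support a superiority conclusion alone, so the same effect has two chances of being declared, and the plan names no mechanism for keeping the overall error at 5%. Second, with about 15 pairs, chance imbalance between the eyes before treatment moves the two estimates apart. When one interval clears zero and the other does not, the plan does not say whether the superiority question was answered yes or no.

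**Working it through.** **Inputs from the documents.** 15 completers; differences of 5, 7.5 and 10 points; SD 15 and 20; intraclass correlation (ICC) 0.4, 0.6 and 0.8 (section 14.2). Success is a lower two-sided 95% limit above 0 (section 14.5), which is 2.5% in the superiority direction for each test.

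**Input not in the documents.** r, the correlation between the pre- and post-treatment between-eye differences. I vary it.

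**Reproducing the plan's figure.** For a paired t test, SD of the difference = SD × √(2(1−ICC)) = 15 × √0.4 = 9.49. SE = 9.49/√15 = 2.45, so noncentrality = 7.5/2.45 = 3.06 on 14 df. This gives Table 3's 0.897, but only at a one-sided level of 0.05, and all 18 cells of Table 3 match on that basis. With the planned two-sided 95% interval the power is 0.812. That mismatch is a separate matter; below I use the interval rule.

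**Correlation of the two tests.** Let D0 and D1 be the between-eye differences before and after treatment, each with variance σ². Hypothesis 1 uses D1; hypothesis 2 uses D1 − D0.

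- Cov(D1, D1 − D0) = σ²(1−r) and Var(D1 − D0) = 2σ²(1−r).
- The correlation is (1−r)/√(2(1−r)) = √((1−r)/2).
- If one common covariance c holds across both eyes and both times, Cov(D1, D0) = c − c − c + c = 0, so r = 0.

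**False-positive chance, superiority direction, one time point.** Simulated paired t tests, n = 15, 200,000 runs, regions taken as independent:

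| r | test correlation | one region, either scale | one region, both scales | any of three regions, either scale |
|---|---|---|---|---|
| 0 | 0.71 | 4.2% | 0.8% | 12.2% |
| 0.5 | 0.50 | 4.6% | 0.4% | 13.2% |
| 0.8 | 0.32 | 4.75% | 0.2% | 13.6% |
| 0.95 | 0.16 | 4.9% | 0.1% | 14.0% |

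The references for one scale are 2.5% for one region and 1 − 0.975³ = 7.3% for any of three. The ratios run from about 1.7 (4.2/2.5 and 12.2/7.3) to about 1.9. The upper bounds with independent tests are 1 − 0.975² = 4.9% and 1 − 0.975⁶ = 14.1%. Counting a false difference in either direction roughly doubles the one-region figure: 2 × 4.2% = 8.4% at r = 0 and 2 × 4.6% = 9.2% at r = 0.5, so about 8% to 9%.

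**Disagreement when the effect is real.** True effect 7.5 points, ICC 0.8, one region and time point. The SD of the change difference is √(2(1−r)) times that of the raw difference.

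| SD | r | power, raw | power, change | exactly one succeeds |
|---|---|---|---|---|
| 15 | 0 | 0.81 | 0.52 | 33.7% |
| 15 | 0.3 | 0.81 | 0.67 | 26.8% |
| 15 | 0.5 | 0.81 | 0.81 | 22.5% |
| 15 | 0.7 | 0.81 | 0.96 | 19.5% |
| 20 | 0 | 0.57 | 0.33 | 32.6% |
| 20 | 0.5 | 0.57 | 0.57 | 34.1% |
| 20 | 0.7 | 0.57 | 0.79 | 37.6% |

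These are paired t tests within a region, a simplification of the planned mixed models.

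**The case against.** Several parts of the case for leaving the plan alone are sound.

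- **The pair does not break 5% by itself.** Each test spends 2.5% in the superiority direction, so two of them cannot exceed 5% at any correlation. A reader might infer that the raw/change duplication alone breaches section 14.4. For one region and time point it does not, unless that 5% is read as two-sided or as 2.5% in the superiority direction.
- **Much of the 12% to 14% comes from elsewhere.** The unadjusted any-region rule already takes one scale to 7.3%.
- **Inflation is conditional.** The plan numbers its hypotheses and defines no composite primary success. If both scales must succeed in the same region, the chance is 0.1% to 0.8%. A flat statement that the error nearly doubles is not supported. What remains is that each part of section 14.5 concludes superiority from its own interval, and nothing requires both.
- **Disagreement is not contradiction.** It means that one scale succeeds and the other does not. Significant results in opposite directions practically never occurred in the simulations. The primary objective is to evaluate an effect, and two estimates with intervals do inform it.
- **This is a pilot.** Sections 14.1 and 14.2 call it a feasibility and pilot study whose size was not set by a power calculation. That lowers the stakes. But the plan still states decision rules, an overall error rate and power claims, and these should agree with each other.

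**Conclusion.** The point holds in a limited form. Two primary superiority tests of one eye-randomized effect are each run at the full level with no deciding rule. If either suffices, the false-positive chance rises about 1.7 to 1.9 times: to 4.2% to 4.9% from 2.5% for one region and time point, or to about 12% to 14% from 7.3% across three regions. It does not rise if both must succeed in the same region. Separately from any error-rate argument, with a true 7.5-point effect and ICC 0.8 the plan leaves the superiority verdict undefined in between about 19% and 38% of trials for r from 0 to 0.7.

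These sizes rest on the assumed r, 15 complete pairs, equal variances before and after treatment, independent regions and one time point. It is also tempting to infer that the change score should decide because it measures relief from end-of-day discomfort. The documents do not support that choice: it depends on r, and at r = 0 with SD 15 and ICC 0.8 the change score has power 0.52 against 0.81 for the raw score.

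**What to change.** In sections 2.3 and 14.5, do one of the following:

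- Name one scale in advance as the deciding superiority test and make the other supportive.
- Test the two in a fixed order within the same region and time point, so that the second is claimed only where the first succeeded. The matching matters. If success in any region opens the gate, a region with no effect again gets two chances (4.6% at r = 0.5).

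Choose the scale on the expected r and state the reason: the change score has lower power than the raw score below r = 0.5 and higher power above it. If the sponsor means that both must succeed, say so and accept the loss: joint power is about 0.70 against 0.81 for either alone (7.5 points, SD 15, ICC 0.8, r = 0.5). Splitting alpha equally is also valid but cuts power per test from 0.81 to 0.71 for the raw score in the same setting.

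The cost is about one sentence in each section; both analyses are still run and data collection is unchanged. The downside is that a result positive only on the supportive scale can no longer be called a primary success. This removes only the raw/change layer. The three regions and two time points need their own rule before the overall 5% in section 14.4 can be met.
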